IRB	Institutional Review Board
MELAS	mitochondrial encephalomyopathy, lactic acidosis, and stroke-like episodes
NO	nitric oxide
NOS	nitric oxide synthase
nNOS	neuronal nitric oxide synthase
PAECs	Pulmonary arterial endothelial cells
PH	pulmonary hypertension
VLBW	very low birth weight

1.0 Background and Introduction

1.1 Introduction

[figure not shown]
Bronchopulmonary dysplasia (BPD) is a chronic lung disease that affects up to 35% of very low birth weight infants (VLBW < 1500 g) (1, 2). Based on the current numbers of VLBW infants born annually in the U.S., between 5,000-10,000 neonates will develop BPD each year (3). It is estimated that 8-42% of infants with BPD will develop pulmonary hypertension

(PH)(4-8). Moreover, it has been known since the 1980's that echocardiographic evidence of PH in infants with BPD is associated with up to 40% mortality (9, 10).

Treatment options to ameliorate PH in infants with BPD (BPD-PH) are limited. There have been no randomized clinical trials of any therapy in infants with BPD-PH. The standard care for the management of BPD-PH is to attempt to resolve the underlying lung disorder and the judicious use of oxygen as a potent pulmonary vasodilator (11, 12). Using this management approach, which has not changed since the 1980's, the survival rates for infants with BPD-PH in the 2000's has been reported to be 64% at 6 months and 53% at 2 years after diagnosis of PH (13). The lack of improvement in outcomes for the past 3 decades has led to the widespread agreement that novel and effective therapies are desperately needed for infants with BPD-PH.

1.2 Nitric oxide metabolism

Nitric oxide (NO) is a potent vasodilator synthesized from the amino acid substrate, L-arginine, by one of three NO synthase (NOS) isoforms: neuronal NOS (nNOS), inducible NOS (iNOS), and endothelial NOS (eNOS). L-citrulline provides an intracellular source for L-arginine via a two-step biosynthetic pathway, involving the co-substrate, aspartate and the enzymes arginosuccinate synthetase (ASS) and arginine succinate lyase (ASL). Through this recycling pathway, L-citrulline serves as both a substrate for arginine and as the end product when arginine is converted to NO by NOS. Thus, L-citrulline provides an approach to deliver bioavailable L-arginine to synthesize NO. A simplified diagram of the L-citrulline-L-arginine-NO pathway is shown below:

1.3 Nitric oxide and Pulmonary Hypertension

Evidence that impaired NO signaling plays a pivotal role in the pathobiology of PH in humans is now well established (14-17). There is evidence that inhaled NO (iNO) may be beneficial for the treatment of infants with BPD-PH. In particular, iNO has been shown to function as an acute pulmonary vasodilator in infants with BPD-PH (18, 19). There is also some data showing clinical improvement when iNO is used long term, for 8-90 days (20). Use of iNO is expensive and cumbersome especially when used long-term. The responsiveness to iNO

suggests that other agents that improve NO bioavailability might have beneficial effects in infants with BPD-PH.

Administering L-arginine, the amino acid substrate for NO synthesis, has been studied as a therapy to improve NO signaling and ameliorate PH. We, and other investigators, have shown that limited bioavailability of L-arginine contributes to vascular dysfunction in PH (21-23). Unfortunately, results with L-arginine supplementation have not been consistent, with some studies showing no benefit from either acute (24) or prolonged (25) L-arginine supplementation in animals or humans with PH. In addition, the feasibility and logic of chronic oral L-arginine supplementation are questionable, because the presence of arginase in gut bacteria, intestinal epithelial cells, and hepatocytes dictates that orally administered L-arginine will be largely catabolized to ornithine and urea. This catabolic loss of L-arginine necessitates the administration of massive L-arginine doses to achieve increases in circulating levels that are therapeutically effective (26). These large doses are often poorly tolerated and patient compliance can be difficult to maintain (27). Thus, alternative means of increasing NO production merit investigation.

1.4 Citrulline and Nitric Oxide

Unlike arginine, L-citrulline is not subject to presystemic breakdown in the gut. Instead, L-citrulline is produced and released into the circulation by enterocytes. Adult humans who receive oral L-citrulline achieve dramatic elevations in circulating L-citrulline, with minimal urinary losses (28-30). The bioavailability of oral L-citrulline has also been demonstrated in newborn piglets (31).

Pulmonary arterial endothelial cells (PAECs) express ASS, ASL, and eNOS and can, therefore, use L-citrulline to produce NO (32). In studies with piglet PAECs, we showed that L-citrulline treatment increases NO production in PAECs cultured under both normoxic and hypoxic conditions (33). Moreover, in our newborn piglet model of chronic hypoxia-induced pulmonary hypertension, L-citrulline supplementation was shown to increase plasma and tissue concentrations of citrulline, improve pulmonary vascular NO production, and ameliorate the development of pulmonary hypertension (31). Thus, the presence of the enzymes needed to produce L-arginine-NO from L-citrulline in PAECs affords the opportunity to use L-citrulline supplementation to increase NO bioavailability in the pulmonary vasculature and ameliorate pulmonary hypertension. Additional rationale to evaluate the impact on pulmonary hypertension from oral L-citrulline supplementation is provided by a recent study showing that plasma L-citrulline levels were lower in infants with BPD-PH than in infants with BPD and no PH (34).

1.5 Oral L-citrulline supplementation and previous human and animal studies

Long-term treatment options are needed for infants and children with chronic conditions, such as those with BPD. Intravenous therapies are difficult to maintain and are fraught with complications when used long-term. Infants and children with certain types of urea cycle defects receive oral L-citrulline replacement therapy for decades and show no evidence of toxicity from its use (35, 36). A study recently performed in children, ages 4 to 16 years, with

mitochondrial encephalomyopathy, lactic acidosis, and stroke-like episodes (MELAS) syndrome reported 5 fold increases in plasma L-citrulline (increase from 21 to 156 μ M) and 3 fold increases in NO synthesis with the administration of oral L-citrulline (dose of 10 g/m² body surface area/day if weight >20 kg and 500 mg/kg/dose if weight < 20 kg) every 4 hours for 48 hours (37). Of note, no adverse effects were found indicating that oral L-citrulline doses up to 3 g/kg/d (500 mg/kg/dose given every 4 hours) are safe and tolerated in infants and children (37). However, the pharmacokinetics of oral L-citrulline has not been evaluated in infants or children.

The role of oral L-citrulline supplementation has been under studied in infants and children with cardiovascular disease. A pilot phase two clinical trial in children with sickle cell disease showed that oral L-citrulline given twice daily in doses of 0.1 g/kg decreased vascular complications and improved the symptoms of well-being (38). Supplementation with oral L-citrulline using perioperative doses of 1.9 g/m² (approximately 0.13 g/kg given every 12 hours for a total of 5 doses), was found to be well tolerated and safe in children, ages 0.3-29 months, undergoing cardiopulmonary bypass at risk for development of postoperative pulmonary hypertension (39). Notably, postoperative pulmonary hypertension did not develop in those children who had naturally elevated levels of citrulline or who achieved plasma citrulline levels greater than 37 μ M with the oral L-citrulline supplementation, reflecting an approx. 50-100% increase from their basal L-citrulline levels. In our newborn piglet model we found that the development of chronic hypoxia-induced pulmonary hypertension was ameliorated in piglets treated with an oral dosing strategy that achieved increases in trough plasma L-citrulline that were 50-100% above baseline levels (total daily dosing of 0.26-0.52 g/kg/d) (31, 40). However, piglets treated with a higher oral L-citrulline dose strategy (total daily dosing of 1-1.5 g/kg/d) achieved a 3-5 fold increase in trough plasma L-citrulline and had a more marked reduction in chronic hypoxia-induced pulmonary hypertension than did piglets treated with the lower dose strategy (31). These findings in our newborn pig model provide proof of concept to test the efficacy of using chronic oral L-citrulline to treat human infants at high risk of developing pulmonary hypertension in conditions that are associated with intermittent or persistent hypoxia, such as BPD. In addition, our pre-clinical studies in newborn piglets and the clinical study in infants and children undergoing cardiac bypass surgery suggest targeting a circulating plasma L-citrulline trough that is at least 100%, and perhaps 3-5 fold, above basal levels. Based on published plasma L-citrulline levels of 13-70 μ M in infants and children (41), the dose and interval of L-citrulline treatment should target trough L-citrulline plasma levels of approx. 100-150 μ M. Moreover, total daily doses of 3 g/kg/d (500 mg/kg/dose given every 4 hours) were recently shown to be safe and tolerated in infants and children (37).

Pharmacokinetic dose-finding, tolerability studies of oral L-citrulline in infants at high risk of developing BPD-PH are needed to determine appropriate dosing strategies (dosing ranges and treatment intervals) before use in large scale efficacy treatment trials for BPD-PH.

Of note, the first phase of this study has now been completed and the data reveals basal plasma L-citrulline levels of 9-36 μ M, with a mean of 28 +/- 8 μ M for infants in this study (infants at high risk of developing BPD-PH). Therefore, for infants at high risk of developing BPD-PH, the appropriate plasma L-citrulline trough to target is a level that is 50-100% above basal

levels of approx. 9-36 μ M. Therefore, the trough L-citrulline plasma level to target for patients in this study has been revised from approx. 100-150 μ M to approx. 50-80 μ M.

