1.6 Hypothesis, what is being proposed, and value provided

The hypothesis is that oral L-citrulline will be well tolerated, without significant adverse effects in infants at high risk of developing pulmonary hypertension (PH) associated with BPD. We propose to first characterize the PK profile of oral L-citrulline in order to define an appropriate dose range and treatment interval for infants at high risk of developing BPD-PH. Then using the doses and intervals generated by the PK profile, with a maximum dose of 3 g/kg/d (37), we propose to evaluate the tolerability and ability to achieve the target trough L-citrulline plasma level of approx. 50-80 μ M in patients at high risk of developing BPD-PH treated for 72 hours with oral L-citrulline. These studies will provide the data needed to design a full-scale randomized multi-center trial to evaluate the efficacy of oral L-citrulline therapy to ameliorate BPD-PH in human infants, a patient population that has a desperate need of new therapies.

2. Purpose and Objectives

2.1 Specific Goals of this Proposal:

The goal is to develop oral L-citrulline clinically for the treatment of pediatric pulmonary hypertension associated with bronchopulmonary dysplasia (BPD-PH); before pursuing a large scale treatment trial, pharmacokinetic dose-finding, tolerability studies in patients at high risk of developing BPD-PH are warranted.

2.2 Objectives:

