- For Group 1: one blood draw will be pre-dose and 2 blood draws will be post-dose. The pre-dose blood draw will occur 24-48 hours prior to administering the dose of oral L-citrulline and the two post-dose draws will occur at 1 hours (+/- 10 minutes) and 2.5 hours (+/- 10 minutes) post-dose.
- For group 2: one blood draw will be pre-dose and 2 blood draws will be post-dose. The pre-dose blood draw will occur 24-48 hours prior to administering the dose of oral L-citrulline and the two post-dose draws will occur at 15 minutes (+/- 10 minutes) and 3 hours (+/- 10 minutes) post-dose

These sampling times are designed to estimate the population PK parameters of a typical infant using scaling and population PK analysis of available oral PK profiles in adults (28).

The single dose pharmacokinetic studies have been completed. PK data from 10 subjects (5 in group 1 and 5 in group 2) were analyzed and assessed as being sufficient to provide the information needed to design the next phase, the steady state pharmacokinetic studies.

5.3.2 Steady-state pharmacokinetic studies:

To evaluate the tolerability and ability to achieve target trough L-citrulline levels of 50-80 μ M, an additional group of 18 infants (group 3) will be given oral L-citrulline doses at intervals over a total of 72 hours. The L-citrulline will be provided by Asklepiion Pharmaceuticals. If the participant is not nipple feeding, the dose will be

delivered via the participant's indwelling gavage feeding tube. The dose and interval of L-citrulline are based on results from the studies that assessed pharmacokinetic parameters using a maximum daily dose of 3 g/kg/d. The choice of the maximum daily dose is based on a recent study that showed good tolerability and reported no adverse effects in children with mitochondrial encephalomyopathy, lactic acidosis and stroke-like episodes (MELAS syndrome) treated with oral l-citrulline at a dose of 3 g/kg/d (500 mg/kg/dose given every 4 hours) (37).

Based on results from the single dose pharmacokinetic studies, the infants in group 3 will be given oral L-citrulline doses of 60 mg/kg every 6 hours +/- 30 minutes (4 times a day) for 72 hours (total of 12 doses). This is a total daily dose of 240 mg/kg/day.

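### Does the inconsistent account of the regimen behind the 3 g/kg/d maximum call for a change to the plan?

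*Combined protocol and SAP*

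**What the plan says.** Section 1.5 introduces the source as "A study recently performed in children, ages 4 to 16 years", all with a mitochondrial disorder. It gives the regimen as "dose of 10 g/m² body surface area/day if weight >20 kg and 500 mg/kg/dose if weight < 20 kg", every 4 hours for 48 hours. The same sentence reports plasma citrulline rising from 21 to 156 μM and calls this a five-fold increase. The section then infers that "doses up to 3 g/kg/d (500 mg/kg/dose given every 4 hours) are safe and tolerated in infants and children", and repeats the inference after the piglet and cardiac-surgery evidence.

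The figure reappears twice as a limit. Section 1.6 proposes doses and intervals taken from the PK profile "with a maximum dose of 3 g/kg/d". Section 5.3.2 says the Group 3 dose rests on the single-dose results "using a maximum daily dose of 3 g/kg/d", and here describes the cited study as one in children, without mentioning infants.

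Section 5.3.2 fixes the Group 3 dose at 60 mg/kg every 6 hours, 240 mg/kg/d, for 12 doses. Section 6 repeats that dose and says the final population PK model has been determined.

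**The concern.** One regimen is stated in two time units on either side of a 20 kg cut-off, and the daily dose per kilogram changes several-fold across it. That pattern suggests a per-day/per-dose slip in one part. If the slip is in the lower-weight part, the figure adopted as this trial's maximum would be six times what the source used (3 against 0.5 g/kg/d). The fold-change in the same sentence does not match its own concentrations, which makes a transcription problem more likely.

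The population is the second difficulty. A 48-hour study in children of 4 years and over is offered as evidence of safety in infants, in a protocol that enrols preterm infants at about 32 weeks postmenstrual age. If the maximum governed a dose still to be chosen, a faulty unit or an unsupported safety statement could matter to participants.

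**Working it through.** **Inputs.** From section 1.5: 10 g/m² per day above 20 kg; 500 mg/kg per dose every 4 hours below it; 21 and 156 μM; about 0.13 g/kg every 12 hours in the cardiac-surgery study (ages 0.3 to 29 months). From section 5.3.2: 60 mg/kg every 6 hours. Body surface at 20 kg is not in the documents; I assume 0.80 m² and show 0.70 to 0.90 m².

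**The plan's own figure.** 500 mg/kg × 24/4 = 3,000 mg/kg/d = 3 g/kg/d. It reproduces.

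**The jump at 20 kg.** Upper part: 10 × 0.80 / 20 = 0.40 g/kg/d. Lower part: 3 g/kg/d. Ratio: 3 / 0.40 = 7.5. For 0.85 and 0.75 m² the ratio is 7.1 and 8.0; for 0.90 and 0.70 m² it is 6.7 and 8.6.

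**Putting both parts in one unit (0.80 m²).**
- Both per day: 0.5 / 0.40 = 1.25.
- Both per dose: 10 × 0.80 × 6 / 20 = 2.4 g/kg/d, and 3 / 2.4 = 1.25.

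Either correction removes most of the jump. Under the second, 3 g/kg/d stands. The documents cannot show which part is misprinted.

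**Fold-change.** 156 / 21 = 7.4 times baseline; (156 − 21) / 21 = 6.4 as an increase. Neither is 5.

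**Does any reading reach the dose given?** Group 3: 60 × 4 = 240 mg/kg/d = 0.24 g/kg/d.

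| Reading of the cited regimen at 20 kg | g/kg/d | Group 3 dose as a share |
|---|---|---|
| Lower part as printed | 3.0 | 8% |
| Upper part per dose (0.80 m²) | 2.4 | 10% |
| Lower part per day | 0.5 | 48% |
| Upper part as printed (0.80 m²) | 0.40 | 60% |
| Upper part as printed (0.70 m²) | 0.35 | 69% |

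Per kilogram, the upper part falls in heavier children. At 60 kg and an assumed 170 cm it is 0.281 g/kg/d, still above 0.24. The cardiac-surgery regimen is 0.13 × 2 = 0.26 g/kg/d, so the Group 3 daily dose is 0.24 / 0.26 = 92% of that, although given for longer (72 hours, against 5 doses at 12-hour intervals).

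**Is the maximum used elsewhere?** It bounds the PK-derived dose in sections 1.6 and 5.3.2. The dosing plan in section 6 is built on the 50-80 μM trough target and does not mention it. At 3 / 0.24 = 12.5 times the chosen dose, the maximum did not bind, and none of the readings above would have made it bind. Groups 1 and 2 received a single 150 mg/kg dose, 5% of 3 g/kg, and are complete.

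**The case for a change.** The strongest opposing case is that 3 g/kg/d is operative text. Two sections state it as the maximum, section 5.3.2 rests it on this study alone, section 6 still allows model refinement, and section 1.6 says the results will inform a full-scale trial. On this view an unsupported limit for preterm infants should not be left in place.

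Part of this stands. The regimen is printed in mixed units, the fold-change is wrong on its own numbers, and the ages given do not support a statement about infants. The one cited study with infant ages and a stated dose used 0.26 g/kg/d, which is 3 / 0.26 = 11.5 times lower. The urea-cycle experience mentions infants but gives no dose. Section 1.5 in both places, section 1.6 and section 5.3.2 must be reconciled against the source if the figure is relied on again.

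The consequence does not stand. Refinement in section 6 concerns agreement between predicted and observed troughs; it does not permit a further dose in this study. No section carries 3 g/kg/d into the later trial, which would need its own dose justification. Participants are also covered by the monitoring and withdrawal rules in section 5.3.6 and by DSMB review after the first three in each phase (section 6.1).

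Nor does scaling the troughs strengthen the case. Taking the 28 μM basal mean and the 50-80 μM target, 28 + 12.5 × 22 and 28 + 12.5 × 52 give about 303 to 678 μM, against the reported 156 μM. But 50-80 μM is a target rather than an observation, the sampling time of the 156 μM level is not stated, that level comes from a study with two weight-based regimens, and linearity is assumed.

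**Conclusion.** The inconsistency is real but clerical, and it sits in background text. The jump at 20 kg is about 7- to 8-fold if body surface is 0.75 to 0.85 m². It is implausible rather than strictly contradictory, since the two parts apply to different weights, and the documents leave open whether 3 g/kg/d survives a correction. The extension to infants goes beyond the ages the protocol itself reports.

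No change to the plan follows, because there is nothing to gain in conduct or inference. Dose selection is complete, the Group 3 dose is 8% of the maximum and lower than each reading examined, and neither the trough target nor the PK model depends on the disputed figure. This rests on the dose staying fixed as sections 5.3.2 and 6 state, and on the assumed body surfaces. Over the whole assumed range at 20 kg, the Group 3 dose stays below the lowest reading (0.24 against 0.35 g/kg/d).

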1.6 Hypothesis, what is being proposed, and value provided

The hypothesis is that oral L-citrulline will be well tolerated, without significant adverse effects in infants at high risk of developing pulmonary hypertension (PH) associated with BPD. We propose to first characterize the PK profile of oral L-citrulline in order to define an appropriate dose range and treatment interval for infants at high risk of developing BPD-PH. Then using the doses and intervals generated by the PK profile, with a maximum dose of 3 g/kg/d (37), we propose to evaluate the tolerability and ability to achieve the target trough L-citrulline plasma level of approx. 50-80 μ M in patients at high risk of developing BPD-PH treated for 72 hours with oral L-citrulline. These studies will provide the data needed to design a full-scale randomized multi-center trial to evaluate the efficacy of oral L-citrulline therapy to ameliorate BPD-PH in human infants, a patient population that has a desperate need of new therapies.

2. Purpose and Objectives

2.1 Specific Goals of this Proposal:

The goal is to develop oral L-citrulline clinically for the treatment of pediatric pulmonary hypertension associated with bronchopulmonary dysplasia (BPD-PH); before pursuing a large scale treatment trial, pharmacokinetic dose-finding, tolerability studies in patients at high risk of developing BPD-PH are warranted.

2.2 Objectives:

2.2.1 Primary Objectives

- To characterize the pharmacokinetic profile of oral L-citrulline in infants at high risk of developing BPD-PH in order to define an appropriate dose range (dose and treatment interval that achieves trough L-citrulline levels of approx. 50-80 μ M)
- To evaluate the tolerability and ability to achieve the target L-citrulline plasma level of approx. 50-80 μ M in patients at high risk of developing BPD-PH treated for 72 hours with oral L-citrulline

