2.2.2 Secondary Objective

- To assess the effect of L-citrulline administration on urinary nitric oxide metabolite (nitrite/nitrate) levels in patients at high risk of developing BPD-PH

3. Study Population

3.1 Age of Participants:

32 +/- 1 week postmenstrual age

3.2 Sample Size:

28 participants: 10* participants for pharmacokinetic profile characterization and 18 participants for evaluating the tolerability and ability to achieve target trough plasma levels

- Group 1: 5 participants
- Group 2: 5 participants
- Group 3: 18 participants

* Note that the total participant size for Groups 1 and 2 has been reduced from the originally proposed total of 18 participants to 10 participants. This change was made based on the single patient PK analysis on the 10 enrolled participants. This analysis was assessed to be sufficient to perform the population PK modeling needed to design the next phase of the study. Both the DSMB and the FDA approved the change in participant size.

3.3 Inclusion Criteria:

1. Infants born prematurely at \leq 28 weeks gestation requiring invasive (mechanical ventilation) or non-invasive positive pressure support (nasal continuous positive airway pressure, high flow nasal cannula \geq 1 lpm) at 32 +/- 1 weeks postmenstrual age
2. Tolerating at least one-half of full volume oral/gavage tube feedings (using 120 ml/kg/d as full volume oral/gavage tube feedings)
3. The continuous need for some form of respiratory support (supplemental oxygen and/or flow, or mechanical ventilation) for the prior 14 days
4. Hemoglobin \geq 10 mg/dL

3.4 Exclusion Criteria:

1. Known major fetal anomaly or chromosomal aneuploidy
2. Clinical evidence of congenital heart disease (except patent ductus arteriosus, atrial septal defect, or ventricular septal defect [PDA, ASD, VSD])
3. Urine output < 1 ml/kg/hr
4. History of or known to have liver failure
5. History of or known to have necrotizing enterocolitis
6. History of or known to have significant feeding intolerance beyond the first week of life
7. Presence of any acute illness defined by fever >100.4F, vomiting, or diarrhea
8. Hemoglobin < 10 mg/dL
9. NICU cases determined to be futile (anticipated death prior to hospital discharge)
10. Multiple births

4. Design

Study to Assess Pharmacokinetics of L-Citrulline in infants at high risk of developing pulmonary hypertension associated with Bronchopulmonary Dysplasia

5. Study Procedures

5.1 Recruitment/Participant Identification Process:

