5.3.6 Participant monitoring

All participants will be monitored for clinical evidence of necrotizing enterocolitis, gastrointestinal bleeding, sepsis, feeding intolerance (including vomiting and diarrhea), electrolyte disturbances, hemodynamics, alteration of hematological parameters and death. Any electrolytes, hematologic laboratories, and eye examinations that are ordered as part of standard of care by the participants clinical care team will be monitored. Hypotensive subjects (defined as a decrease in mean arterial blood pressure of more than 25% baseline) will be treated with pharmacological/volume supplementation interventions at the discretion of the attending physician. Treatment unresponsive hypotensive subjects will be withdrawn from the study. Subjects who develop significant feeding intolerance will be withdrawn from the study. Infants who are made NPO for a time period long enough that they miss any doses of L-citrulline will be withdrawn from the study.

6. Statistical Methods, Data Analysis and Interpretation

After the first 3 participants are enrolled in the single-dose PK study (3 participants enrolled in either Group 1 or Group 2), and after the first 3 participants are enrolled in the steady-state pharmacokinetic study (3 participants enrolled in Group 3), an initial PK analysis will be performed and the data will be reviewed by the DSMB to assess for safety to continue the single dose PK study and to continue the steady-state pharmacokinetic study.

Throughout the study, participants who are withdrawn from treatment due to adverse events will be replaced for PK analysis.

Data collected from this study will be examined to ensure that all participants in the analysis meet inclusion criteria. Summary statistical analysis will be conducted to describe participant demographics, citrulline dosing, and participant PK profiles. Outliers in the measured citrulline levels that may influence the estimation of PK parameters will be evaluated. A population model will be developed to describe the citrulline PK and population variability.

The non-linear mixed effect modeling software NONMEM® version 7.3.0 (ICON Development Solutions, [name], USA) will be used to develop models. Perl-speaks-

NONMEM (PsN) 4.4.0, Pirana 2.9.0, and R packages (version 3.2.1) will be used to facilitate, evaluate, and visualize the model development.

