The model development process would include two major steps: base model structure evaluation and covariate screening. The development of a base structural model will include the evaluation of compartment numbers, baseline effects, absorption and elimination kinetics. The stochastic models describing between-subject variability in PK parameters and intra-subject variability in observations will be also examined.

Potential covariates that are predictive of citrulline PK variability will be screened using the stepwise covariate model (scm) building tool of PsN. The continuous covariates to be examined will include, but not be limited to, body weight, length, postnatal age, gestational age, etc. Categorical covariates to be examined will include, but not be limited to, sex, race, ethnicity, and concomitant medication (yes/no). The predefined parameter-covariate association for continuous covariates will be included as a power relation, while categorical covariates will be linearly included. Both stepwise forward selection and backward elimination will be incorporated for covariate searching. Changes in OFV will be considered significant at $p<0.05$ (χ^2 -distribution, 1 df, Δ OFV > 3.84) during forward selection, and $p<0.01$ (1 df, Δ OFV > 6.63) during backward elimination. In addition to the aforementioned statistical criteria, the following standard diagnostic plots will also be used to visually assess the final covariate model fit: observed concentrations versus population- and individual-predicted concentrations, conditional weighted residuals versus time and population-predicted concentrations. To assess the model stability, a nonparametric bootstrap analysis will be conducted. The visual predictive check (VPC) will be performed to further evaluate the final model performance.

Once the final population PK model is determined, an optimal dosing plan will be developed using the model to achieve target plasma trough concentrations of 50-80 μ M in patients at high risk of developing BPD-PH. Statistical comparison between actual trough concentrations and model predicted concentrations will be conducted. Model prediction capability will be evaluated and refinement will be performed.

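### Do the early-withdrawal and replacement rules leave Group 3 tolerability without a usable denominator?

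*Combined protocol and SAP*

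**What the plan says.** Section 2.2.1 joins two aims in its second primary objective, tolerability and reaching the target plasma level, "in patients at high risk of developing BPD-PH treated for 72 hours with oral L-citrulline". Section 3.2 assigns one number to both: "18 participants for evaluating the tolerability and ability to achieve target trough plasma levels". Section 5.3.2 describes the regimen in the same terms: "an additional group of 18 infants (group 3) will be given oral L-citrulline doses at intervals over a total of 72 hours". The trough sample is drawn shortly before the last of the 12 doses.

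Section 5.3.6 removes some infants before then. "Subjects who develop significant feeding intolerance will be withdrawn from the study", as are infants whose hypotension does not respond to treatment. The third rule concerns missed doses: "Infants who are made NPO for a time period long enough that they miss any doses of L-citrulline will be withdrawn from the study". Section 6 then states that "participants who are withdrawn from treatment due to adverse events will be replaced for PK analysis".

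On analysis, Section 6 says "Summary statistical analysis will be conducted to describe participant demographics, citrulline dosing, and participant PK profiles". After the population model it adds "Statistical comparison between actual trough concentrations and model predicted concentrations will be conducted". It lists no summary of tolerability. Elsewhere, Section 5.3.6 monitors all participants for a list of clinical events, Section 6.1 sends early data to the DSMB, and Section 7.4.1 sets adverse event reporting to 48 hours after the last dose.

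**The concern.** Feeding intolerance and hypotension are tolerability outcomes, and they are also reasons for leaving early. An infant who leaves before the last dose has no trough and is not treated for 72 hours. If the objective's wording is taken as the definition of the analysis set, infants withdrawn for intolerance drop out of the tolerability result, and their replacements bring the count back to 18. The result would then look better than the experience of the infants who were dosed.

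The text also seems to leave this open. One number serves two endpoints that need different sets once anyone is withdrawn, and the statistical section names neither a table nor a denominator for tolerability. Section 1.6 says these data will be used to design a randomised efficacy trial, so a flattering tolerability figure would carry forward.

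**Working it through.** **The plan's own figures.** Section 3.2: 5 + 5 + 18 = 28, as stated. Section 5.3.2: 72 h / 6 h = 12 doses, as stated. The twelfth dose falls at 11 x 6 = 66 h, so an infant withdrawn before about hour 66 gives no trough. The documents give no power, precision target or withdrawal rate for the 18, so there is no sample-size calculation to reproduce.

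**How often would the two counts differ?** The withdrawal rate p is an assumption, shown as a range and taken as the same and independent across infants. The chance of at least one withdrawal among 18 is 1 - (1 - p)^18. If every withdrawal preceded the trough and was replaced, the expected number dosed to obtain 18 troughs is 18/(1 - p).

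| Assumed p | Chance of at least one | Expected number dosed |
|---|---|---|
| 2% | 1 - 0.98^18 = 30% | 18/0.98 = 18.4 |
| 5% | 1 - 0.95^18 = 60% | 18/0.95 = 18.9 |
| 10% | 1 - 0.90^18 = 85% | 18/0.90 = 20.0 |
| 20% | 1 - 0.80^18 = 98% | 18/0.80 = 22.5 |

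The last column is an upper figure, because Section 6 replaces only withdrawals due to adverse events. These are chances that two counts differ. They are not chances that tolerability is misreported.

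**What each reading would report.** Suppose k infants are withdrawn for adverse events before the trough and all are replaced, so that 18 + k are dosed. Intervals are exact (Clopper-Pearson) 95%.

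| k | All dosed infants | 72-hour completers only |
|---|---|---|
| 1 | 1/19 = 5.3% (0.1 to 26.0) | 0/18 (0 to 18.5) |
| 2 | 2/20 = 10.0% (1.2 to 31.7) | 0/18 (0 to 18.5) |
| 3 | 3/21 = 14.3% (3.0 to 36.3) | 0/18 (0 to 18.5) |

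The right-hand column would be misleading, so the question is whether the plan leads there.

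**Which reading does the text support?**

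- Sections 2.2.1 and 5.3.2 describe what infants are scheduled to receive, and Section 3.2 is a recruitment number. None makes completion a condition of being analysed.
- The tolerability hypothesis in Section 1.6 is stated for infants at high risk of BPD-PH, with no completion condition, although a later sentence there repeats the 72-hour wording.
- The replacement rule is confined to the PK analysis. It restores the number of troughs and does not remove the withdrawn infant from anything else.
- Monitoring under Section 5.3.6 covers all participants. The reporting window in Section 7.4.1 starts at the last dose actually given, so it applies to infants who stop early.

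Followed as written, the plan keeps withdrawn infants in the safety data. The completers-only column needs an extra step, discarding infants because they were intolerant, and no section calls for it.

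**Does unclear replacement matter to the rate?** Very little. One withdrawal is 1/18 = 5.6% if not replaced and 1/19 = 5.3% if replaced.

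**The case for a change.** The strongest case for a change is that a primary objective should not depend on inference. Section 6 sets out the PK modelling in detail and gives nothing for tolerability: no endpoint, table or denominator. That omission stands even if nobody is withdrawn. Event listings will contain the withdrawn infants, but a listing does not fix a denominator. Replacement is stated only for adverse-event withdrawals, so an infant kept off feeds for another reason could leave 18 dosed and 17 troughs. Section 5.3.6 speaks of leaving the study and Section 6 of leaving treatment, which leaves some doubt about observation afterwards. A few sentences and one table would settle all of this without extra infants or blood.

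The omission is real, and so are the unstated replacement rule for other withdrawals and the mismatch in withdrawal wording. What does not stand is the step from there to a biased result. The documents set no tolerability threshold and no decision based on an event rate, so nothing planned turns on whether the denominator is 18 or 19. The planned dosing summary would show incomplete courses. The withdrawal wording is an editorial matter, since Section 7.4.1 makes no exception for withdrawn infants. A target of 18 with a replacement rule ordinarily means that more than 18 may be dosed, so there is no contradiction in the number.

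**Conclusion.** No change to the plan is needed. The gap is missing detail: an unwritten set definition and an unlisted table. Analysts would fill it in the usual way, with tolerability in every Group 3 infant given a dose and trough results in infants with the sample before the last dose. The parts of the plan that bear on the choice (PK-only replacement, monitoring of all participants, a safety window tied to the last dose) point the same way.

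The two counts are likely to differ if withdrawal is at all common: 60% at an assumed 5% rate, 85% at 10%. The consequence is that two results carry different Ns. With one or two replaced withdrawals the tolerability figure is 1/19 or 2/20, and with none it is 0/18, which excludes only rates above 18.5%. That imprecision comes from the small group, and defining the set in writing would not reduce it.

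This conclusion rests on reading the 72 hours as planned duration and on analysts keeping withdrawn infants in the tolerability count. A stated intention to report tolerability in completers only would reverse it, and the documents contain none.
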